7.2.1. Post-Surgical Additional Exclusion Criteria

The patient is to be evaluated post-operatively prior to the initial treatment with the study drug and will be withdrawn prior to treatment with the study drug if any of the following exclusion criteria are met:

1. Patients who, in the opinion of the investigator, are not likely to tolerate the protocol's allowed analgesic regimen (tramadol plus non-opioid adjuvants).
2. Patients who have been admitted to the ICU post-surgery or have experienced complications during the surgical procedure that would put them at increased risk from receipt of the investigational product in the opinion of the investigator.
3. The patient is not clinically stable and not able to answer questions and follow commands.
4. The patient has evidence of respiratory insufficiency, such as a respiratory rate that is less than 8 breaths per minute or arterial oxygen saturation by pulse oximetry of less than 90% with supplemental oxygen.
5. Use of 5-HT₃ antagonists (e.g. ondansetron, granisetron, palonosetron) preoperatively, intraoperatively, or postoperatively

7.3. Patient Withdrawal Criteria

If a patient is discontinued from the study prematurely, the Investigator must select the primary reason for discontinuation on the End of Study eCRF. In addition, every effort should be made to complete the assessments listed under the End of Treatment/Discharge from Clinic column on the Schedule of Assessments.

Patients withdrawn from the study will be considered evaluable for statistical assessment.

A patient may be removed from the study for the following medical or administrative reasons:

- **Adverse Event:** If a patient experiences an adverse event that the patient finds unacceptable or that, in the judgment of the Investigator or the Medical Monitor presents an unacceptable consequence or risk to the patient, the patient may be discontinued from further participation in the study. If doses are missed due to an Adverse Event and the event resolves, the patient can resume their scheduled treatment at the discretion of the Investigator. Missed doses should be recorded in the eCRF.
- **Administrative Discontinuation:** After consultation with the Investigator or Medical Monitor, a patient may be discontinued from the study for failure to comply with protocol requirements. All instances of noncompliance must be documented in the eCRF.
- **Refusal of Assessments:** If for any reason, following dosing, the patient refuses further assessment during the study, the patient shall be discontinued from the study and the reasons for refusal documented. Reasonable efforts shall be made to monitor the patient for adverse events following such discontinuation. Such efforts shall be documented.

8. TREATMENT OF PATIENTS

8.1. Description of Study Drug

Investigational product will be packaged in identical ampoules containing 1ml of AVE-901. Each ampoule of AVE-901 contains 50 mg of tramadol hydrochloride and sodium acetate trihydrate as buffering agent diluted in water. Ampoules will be packaged in bulk cartons.

Study drugs will be distributed to the clinic using a designated distribution center. The Sponsor will provide the investigator with adequate quantities of investigational product and supplies to conduct the study. Specific details regarding investigational product supplies, dose preparation, and accountability will be described in a pharmacy manual at the clinic.

Table 5 provides a summary description of the drug products, including the dosage form, the unit dose, and a physical description of the product.

Table 5: Investigational Product (Study AVE-901-104)

	Investigational Product
Product Name:	Tramadol for infusion 50 mg
Dosage Form:	Liquid
Unit Dose:	50 mg/1mL ampoule
Route of Administration:	Intravenous infusion
Physical Description:	Clear solution
Manufacturer:	Siegfried Hameln

8.2. Concomitant Medications

Medications deemed necessary for the patient's welfare are permitted. The following drugs are EXCLUDED from use:

- Moderate or strong inhibitors of CYP3A4 or CYP2D, inducers of CYP3A4, drugs which may increase serotonergic tone including SSRIs, SNRIs, tricyclic antidepressants, trazodone, cyclobenzaprine triptans, 5-HT3 antagonists including ondansetron, and amphetamines; and drugs which may lower seizure threshold.
- Any opioid based analgesic (post dosing)

Adverse events (AEs) such as nausea, vomiting and pruritus should be managed using standard of care, excluding medications specifically noted in the study protocol.

Protocol AVE-901-104 Phase 3 Open-Label Safety Study
Avenue Therapeutics, Inc.

Tramadol Infusion
August 29, 2018

8.3. Treatment Compliance

Treatment compliance with study medication during the treatment periods is expected to be high, as patients will be dosed directly in the clinic under well-controlled conditions. The date and time of study drug administration will be recorded on the eCRF.

8.4. Overdose

Tramadol products in excessive doses, either alone or in combination with other CNS depressants, including alcohol, are a cause of drug-related deaths. Acute over dosage with tramadol can be manifested by respiratory depression, somnolence progressing to stupor or coma, skeletal muscle flaccidity, cold and clammy skin, constricted pupils, seizures, bradycardia, hypotension, cardiac arrest, and death. Serious potential consequences of over dosage with tramadol are CNS depression, respiratory depression and death. Some deaths have occurred as a consequence of the accidental ingestion of excessive quantities of tramadol alone or in combination with other drugs, while others were associated with abuse of tramadol. Review of case reports has indicated that the risk of fatal overdose is further increased when tramadol is abused concurrently with alcohol or other CNS depressants, including other opioids (Ultram® Prescribing Information, 2009).

Of note, while naloxone will reverse some, but not all, symptoms caused by over dosage with tramadol, the risk of seizures is also increased with naloxone administration. In animals convulsions following the administration of toxic doses of tramadol could be suppressed with barbiturates or benzodiazepines but were increased with naloxone. Naloxone administration did not change the lethality of an overdose in mice. Hemodialysis is not expected to be helpful in an overdose because it removes less than 7% of the administered dose in a 4-hour dialysis period (Ultram® Prescribing Information, 2009).

Additional details may be found in the Investigator's Brochure.

8.5. Randomization, Blinding and Unblinding

This is an open-label study in which all patients will receive the same treatment. Thus, there is no randomization or blinding applied in this study.

Protocol AVE-901-104 Phase 3 Open-Label Safety Study
Avenue Therapeutics, Inc.

Tramadol Infusion
August 29, 2018

9. STUDY DRUG MATERIALS AND MANAGEMENT

Study drug will be provided to the investigational centers.

9.1. Study Drug Packaging and Labeling

Single-use, glass ampoules with labels and an outer fiberboard carton with a single panel label will have the following information:

1. Protocol #: AVE-901-104
2. Each 1ml ampoule contains 50mg of IV Tramadol (C-IV)
3. Intravenous injection administration only. Use as directed per protocol.
4. Store at 20°C to 25°C (68°F to 77°F). Store away from heat sources and direct sunlight.
5. Caution: New Drug – Limited by Federal (United States) Law to Investigational Use.
6. Sponsor: Avenue Therapeutics, New York, NY 10019
7. Manufactured by: Siegfried Hameln
8. Lot number: _____

The clinical trial supply label will be in accordance with ICH GCP and local requirements for investigational product labelling.

9.2. Packaging, Labeling, and Storage of Clinical Supplies

Investigational products are for investigational use only and the study drug supplied for this study is intended for use only within the context of this study. The study drug supplied for this study should be stored in a secure place and maintained under adequate security until dispensed for patient use or returned to the Sponsor. Tramadol is classified as a Schedule IV controlled drug and security requirements as per 21CFR 1301.71-77 are to be followed at the clinic.

Investigational products should be stored at room temperature (20-25°C or 68-77°F).

Investigational products should be stored away from heat sources and direct sunlight.

The Investigator, pharmacist, or their designee, will verify that study drug supplies are received intact and in the correct amounts by signing and dating the investigational product receipt log. The person receiving the supplies must verify that the shipment contains all the items noted in the shipment inventory. Any damaged or unusable drug in a given shipment will be documented in the study files. The Investigator must notify the Sponsor or designee of any damaged or unusable investigational product supplied to the Investigator's site.

The site will maintain a Drug Inventory Log (includes, but not limited to, the following: lot number, number of units received and number of ampoules dispensed). The site will also maintain patient-specific drug dispensing logs.

An overall accountability of investigational product will be performed and verified throughout the study and at the site closeout visit. Upon completion of the study, copies of the investigational product accountability records will be returned to the Sponsor. All used and unused study drug supplies will be inventoried, accounted, and returned to the Sponsor at the end of the study. By signing the Investigator Agreement page of this protocol, the investigator or

Protocol AVE-901-104 Phase 3 Open-Label Safety Study
Avenue Therapeutics, Inc.

Tramadol Infusion
August 29, 2018

named sub-investigator agrees not to supply study drug to any person(s) not enrolled in the study.

9.3. Study Drug Preparation and Administration

Study drug will be dispensed by the qualified, licensed study personnel and administered to the patient by a licensed designated staff member. The designated personnel will prepare the treatments for administration and maintain accountability records.

AVE-901 will be provided in ampoules containing 1 mL of IV Tramadol. Directions for preparation of study medication will be recorded in the pharmacy manual prior to initiation of the study. The pharmacy manual will provide procedures for preparation (and destruction) that correspond to the dose of study medication used in this study.

9.4. Study Drug Accountability

Patients will be treated at the investigational center and therefore the Pharmacist or other investigational staff via documentation of receipt of the study drug and dosing/treatment given will perform drug accountability.

9.5. Study Drug Handling and Disposal

Records of receipt, dispensing records and inventory forms, as applicable, will be examined and reconciled during and at the end of the study. Both the investigational drug that is used during the course of the study, as well as any remaining unused investigational drug, must be accounted for on a drug accountability record provided to the PI by the Sponsor or its designee. Drug destruction will be completed following the clinical sites SOP on destruction and a destruction certificate will be maintained at the clinic.

If directed and if drug is not destroyed on site, at the end of the study, all unused investigational drug, accompanied by a packing slip will be shipped to designee provided by the sponsor.

In addition, a copy of all completed drug accountability records must be retained in the Investigators' Study Files, with a copy sent to the Sponsor or its designee.

The products are to be stored in a safe place (locked facility) at the appropriate temperature and without exposure to freezing.

Protocol AVE-901-104 Phase 3 Open-Label Safety Study
Avenue Therapeutics, Inc.

Tramadol Infusion
August 29, 2018

10. PHARMACOKINETIC ASSESSMENTS

There are no pharmacokinetic assessments being performed in this study.

11. ASSESSMENT OF SAFETY

11.1. Safety Parameters

Safety assessments will include collection of adverse events. In addition, safety assessments include clinical laboratory tests, vital signs, physical examination, concomitant medications, and 12-lead ECGs.

11.1.1. Demographic/Medical History

Demographic information and medical history will be collected at Screening for determination of eligibility. Demographic information will include the following: age, gender, race and ethnic origin. Significant medical history within the past two years should be recorded on the eCRF.

11.1.2. Vital Signs

Vital sign assessments include blood pressure, pulse, temperature, respiratory rate, and SpO₂, and are collected at varied times as per the Schedule of Events. Vital signs will be performed after the patient has rested sitting or supine for 5 minutes.

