6.6.1. Screening

Screening will occur from Day -28 through Day -1 and will be conducted as a clinic visit. Patients will have the purpose and procedures of the study explained to them and, those who elect to participate in the study, will provide written informed consent and be screened for participation according to the eligibility criteria. Patients will undergo protocol specific education including but not limited to the various post-treatment efficacy and safety measures. The following information and procedures will be performed and documented as part of the screening assessment:

- Demographics, including gender, race and ethnic origin, date of birth, height, weight and calculated BMI.
(https://www.nhlbi.nih.gov/health/educational/lose_wt/BMI/bmicalc.htm)
- Inclusion/exclusion eligibility criteria
- Physical examination
- ASA Physical Status
- Medical history
- Prior and ongoing medications (taken in previous 30 days)
- Vital signs: blood pressure, heart rate, respiratory rate, and oral temperature (after seated or supine for 5 minutes) and SpO₂
- 12-lead ECG (after supine for 5 minutes)
- Blood samples for hematology and clinical chemistry
- Pregnancy test (serum) for women of child-bearing potential
- Urine samples for urinalysis

Compliance with inclusion criteria and exclusion criteria will be verified against information collected and documented in the source documents and the eCRF.

Protocol AVE-901-104 Phase 3 Open-Label Safety Study
Avenue Therapeutics, Inc.

Tramadol Infusion
August 29, 2018

For patients that screen within 5 days of surgery, central laboratory values may not be available to assess eligibility. For these patients it is acceptable for sites to draw local lab to assess eligibility, in addition to the central lab, which will still be used as the baseline in the study. If local labs are used to access eligibility at screening, at a minimum the following analytes must be reviewed from the local laboratory prior to dosing; magnesium, calcium, potassium, sodium, serum creatinine, ALT, AST, hemoglobin. The local laboratory listed on the FDA 1572 Form must be used for all local blood draws.

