6.6.4. Treatment Period/Post Surgery

Patients will receive their first dose of study medication (T₀) within 8 hours of meeting the postsurgical eligibility. Treatment is anticipated to occur from Hours 0 up to Hour 168. The latest (last dose) that is allowed is at Hour 164. Patients will be dosed at Hour T₀, T₂, T₄, and then every 4 hours thereafter, for a total of up to 43 doses administered over the 168-hour treatment period. Assessments will have a ± 10 minute window.

Antiemetic treatments (with the exception of Zofran or other 5-HT₃ antagonists) are allowed.

Treatment period assessments include:

- Recording vital signs including: respiratory rate, heart rate, pulse oximetry (SpO₂), temperature, and blood pressure at 0, 0.5, 1, 2, 3, 4, and then every 4 hours thereafter during the first 48 hours. After 48 hours patients continuing treatment should have vitals taken every 8 hours.
- ECGs will be assessed at screening, post-surgery prior to dosing (T₀), and at 20 to 30 minutes after the start of each infusion for the first 24 hours. With the 10-minute window allowed per assessments, the on-treatment ECGs need to be done between 10 to 40 minutes after the start of each dosing infusion.
- Patient Global Assessment at 24 hours
- Adverse events and concomitant medications will be collected as appropriate.
- Following the first dose of study drug, the patient will be allowed to use non-opioid analgesics if additional pain relief is required. These medications will be captured on the concomitant medications page
- Concomitant medication use

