6.6.5. End of Treatment

At the End of Treatment patients will undergo:

- A brief symptom driven physical examination
- Vital signs: blood pressure, heart rate, respiratory rate, and oral temperature (after seated or supine for 5 minutes) and SpO₂
- 12-lead ECG (after supine for 5 minutes)
- Blood samples for hematology, clinical chemistry, urinalysis, and pregnancy test
- Patient Global Assessment
- AEs
- Concomitant medication use

End of Treatment assessments do not follow a +/- 10 minute window, but just need to be completed prior to discharge

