11.1.4. Electrocardiogram (ECG)

All scheduled ECGs will be performed after the patient has rested supine for approximately 5 minutes as per the schedule of events.

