9.5. Vital Signs

Vital signs results including BP (systolic and diastolic), heart rate, respiration rate, pulse oximetry, and temperature will be listed for individual patients. Baseline for vital signs measurements will be defined as the last evaluation before dosing with study medication. Vital signs and changes from baseline will be summarized by time point.

Vital sign parameter outcomes will be assessed for potential clinical significance; observed values and changes from pre-treatment to on-treatment time points will be tabulated for continuous parameters, as warranted.

The number and percent of patients with potentially clinically significant (PCS) values during the treatment phase will be summarized. A focus will be on new-onset PCS values, i.e., patients with pre-existing PCS values at pre-treatment will not be considered to have new-onset values on-treatment. The criteria for identifying potentially clinically significant vital signs values are provided in Table 4.

Table 4:List of Potentially Clinically Significant Ranges for Vital Sign Parameters
(Study AVE-901-104)

Variable Name	LOW	HIGH

Systolic BP	<86 mm Hg OR a decrease of ≥25 mm Hg from baseline	>200 mm Hg OR an increase of ≥25 mm Hg from baseline
Diastolic BP	<48 mm Hg OR a decrease of ≥20 mm Hg from baseline	>110 mm Hg OR an increase of ≥20 mm Hg from baseline
Heart rate ¹	1) <45 bpm OR a decrease of ≥25 bpm from baseline	1) >105 bpm and increase ≥25 bpm from baseline OR >125 bpm

¹ bpm: beats per minute

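### Vital signs may be taken sitting or supine at each reading, but the SAP flags change from baseline without regard to posture, so a postural difference can be counted as change on AVE-901

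*Protocol*

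**What the plan says.** **Posture.** Protocol 11.1.2 sets the general rule: "Vital signs will be performed after the patient has rested sitting or supine for 5 minutes". Sections 6.6.1, 6.6.2 and 6.6.5 repeat the choice ("after seated or supine for 5 minutes"). Section 6.6.4 schedules the on-treatment sets "at 0, 0.5, 1, 2, 3, 4, and then every 4 hours thereafter during the first 48 hours" and every 8 hours after that, and adds no posture of its own. For ECGs the protocol does fix posture: "All scheduled ECGs will be performed after the patient has rested supine for approximately 5 minutes" (11.1.4).

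**Analysis.** SAP 9.5 defines baseline by time only: "Baseline for vital signs measurements will be defined as the last evaluation before dosing with study medication". It continues: "Vital signs and changes from baseline will be summarized by time point". SAP Table 4 then lists potentially clinically significant (PCS) values. The low systolic criterion is "<86 mm Hg OR a decrease of ≥25 mm Hg from baseline". A systolic rise of 25 mm Hg, a diastolic change of 20 mm Hg in either direction and a heart-rate fall of 25 bpm are likewise each sufficient alone. A heart-rate rise of 25 bpm counts only together with a rate above 105 bpm; a rate above 125 bpm counts by itself.

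**Role.** Vital-sign changes are among the safety endpoints named under the primary objective (Protocol 5, SAP 2.1.1). There is no comparator (SAP 2.5.2).

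**The concern.** A change from baseline can be read as a change in the patient only if both readings are taken under the same conditions. Here the conditions may differ. If a patient is supine for the pre-dose reading and sitting for a later one, or the reverse, the difference in posture becomes part of the recorded change. It then enters both the mean-change table and the PCS flags, and it can create a flag or hide one.

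In a randomised comparison, posture differences would be expected to fall about equally in each arm. This study has one arm, so nothing offsets them, and an analysis that uses no posture variable cannot identify the affected readings. At stake is the interpretation of a named safety endpoint. The data will also be pooled with those of two efficacy studies in an overall safety database (Protocol 4.4).

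**Working it through.** **Plan's own figure.** The documents give no number for a posture effect or for the SD of change. The only computed design figure is the sample-size statement of about 90%. It reproduces (1 − 0.99^250 = 91.9%) but does not bear on this point.

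**Inputs**

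- Systolic cut-off for a fall: 25 mm Hg (SAP Table 4).
- Planned enrolment: about 250 (Protocol 12.1).
- SD of systolic change from baseline: not given; assumed 10 to 15 mm Hg.
- Amount *d* by which the later posture lowers the systolic reading: not given; assumed 5 mm Hg, with 10 mm Hg as a wider case.
- Share *f* of readings taken in a posture different from baseline: not given; left open.

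**Step 1. Readings where posture differs.** Under a normal model with no drug effect, P(fall ≥ 25) = Φ((−25 + d)/SD).

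| SD (mm Hg) | d = 0 | d = 5 | d = 10 |
|---|---|---|---|
| 10 | Φ(−2.50) = 0.6% | Φ(−2.00) = 2.3% | Φ(−1.50) = 6.7% |
| 12 | Φ(−2.08) = 1.9% | Φ(−1.67) = 4.8% | Φ(−1.25) = 10.6% |
| 15 | Φ(−1.67) = 4.8% | Φ(−1.33) = 9.1% | Φ(−1.00) = 15.9% |

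The column d = 0 is also the result when both readings share a posture.

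**Step 2. The other direction.** If the later posture raises the reading by 5 mm Hg, d = −5. The share flagged for a fall drops to Φ(−30/10) = 0.1% at SD 10 and Φ(−30/15) = 2.3% at SD 15, so some falls are hidden. The change in percentage points is not the mirror image of Step 1, because the normal tail is curved.

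**Step 3. Scaling to the study.** The excess share at a time point is f × [P(d) − P(0)]. With d = 5 mm Hg, all affected readings shifted downwards and all 250 patients measured:

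- f = 0.25: 0.25 × (2.3% − 0.6%) × 250 ≈ 1 patient at SD 10; 0.25 × (9.1% − 4.8%) × 250 ≈ 3 at SD 15.
- f = 0.5: about 2 to 5 patients.
- f = 1: about 4 to 11 patients.

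Fewer patients will remain on treatment at later time points. Posture differences in both directions would partly cancel in the mean, but would still add spread and flags. SAP 9.5 also counts patients flagged during the whole treatment phase. There are 16 scheduled readings after T0 up to Hour 48 (0.5, 1, 2, 3 and 4, then 8 to 48 every 4 hours). The per-patient share is therefore higher than the per-reading share, with or without a posture effect. Putting a figure on it would need a correlation and a switching pattern that the documents do not give.

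**The case against.** The strongest reply is that the effect may be small.

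- **Frequency is unknown.** It arises only where posture differs between baseline and a later reading. The ECG rule gives some reason to expect supine vital signs at both ends: a supine ECG is due after surgery before T0 and another at End of Treatment beside the vital signs. In the first 24 hours a supine ECG follows each infusion at 20 to 30 minutes, close to the Hour 0.5 set. This stands as a reason for caution about size. It does not require supine vital signs at any time.
- **Consequences are limited.** The flags are only potentially significant, the analysis is descriptive, individual values are listed, and the absolute limits do not depend on baseline. This also stands. It limits the importance of the point but does not remove it.

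Some stronger readings are tempting, and the documents do not support them.

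- *Posture drifts from supine to sitting as patients recover, so the study will show a spurious trend.* No section describes posture or mobilisation over time, and T0 may be up to 8 hours after post-surgical eligibility is met. The direction is a conjecture.
- *The rates in Step 1 apply to all 250 patients.* That would need every patient to change posture in the same direction.
- *Using the same heart-rate cut-offs in SAP Tables 4 and 5 mixes supine and sitting data.* It does not. ECG heart rate has its own pre-dose baseline and summary under a supine rule, and the two series are never subtracted from each other.
- *A posture change alone will trigger high heart-rate flags.* The change criterion also needs a rate above 105 bpm, so this is less likely than for blood pressure.
- *Posture is not recorded.* The eCRF is not among the documents, so this cannot be asserted. What can be said is that the SAP makes no use of it.

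**Conclusion.** The point holds as a measurement weakness of unknown size. The protocol leaves posture free at each reading, and the SAP flags blood-pressure changes and heart-rate falls on change alone. With no control arm, a postural difference cannot be told apart from a change on AVE-901 in the planned tables.

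Among affected readings, a 5 mm Hg lowering would take the share flagged for a systolic fall from 0.6%–4.8% to 2.3%–9.1%. This rests on the assumed shift, an assumed SD of 10 to 15 mm Hg and a normal model. The study-wide effect is that excess multiplied by the unknown share of affected readings. The sample size is not affected, and no test depends on the result. It is worth correcting because the correction is cheap.

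**What to change.** **Protocol 11.1.2, 6.6.4 and 6.6.5.** Require blood pressure and heart rate to be taken in one posture per patient, from the pre-dose Hour 0 reading through End of Treatment: supine where feasible, as for ECGs. Record the posture with each set.

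**SAP 9.5.** Keep all readings and all PCS flags in the main tables. Mark the change-based flags that come from pairs taken in different postures. Add a sensitivity summary of change from baseline restricted to same-posture pairs. Different-posture readings should not be dropped from the main tables, because in a safety study that could remove real falls.

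**Cost.** One sentence in each of the three protocol sections, one eCRF field if none exists, and one extra table. No additional measurement is needed and the sample size does not change.
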